13.6. Level of significance

Level of significance is not pertinent to this trial as it is a Phase 1 safety and immunogenicity trial.

13.7. Criteria for Termination of the Trial

The Institute of Human Virology and the Principal Investigator reserve the right to discontinue this study for administrative reasons at any time. The trial may also be discontinued if there is insufficient product to continue or if it is determined that the study medication may not be safe for further administration to volunteers. See [Section 6.4.1](#) , [Section 6.5](#) and [Section 7.3](#).

13.8. Procedures for Missing or Spurious Data

Missing or spurious data will be reviewed by appropriate study personnel and the IHV monitors. These personnel will attempt to determine the cause of the missing or spurious data and to clarify the data. Any information that is not obtained as specified in the protocol should be indicated by the designation ND for not done or NA for not applicable. An explanation should be noted on the case report form as to why the required information was not obtained. If illegible or uncertain entries require clarification, the clarification may be printed above the original entry, initialed and dated.

13.9. Changes in Statistical Methods

Any deviation from the original statistical plan will only be done after consultation with a statistician and approval of the sponsor. This is not expected to occur except if it is determined that the original statistical plan is not sufficient or appropriate for the data analyzed.

14. DIRECT ACCESS TO SOURCE DATA/DOCUMENTS

14.1. Study Monitoring

Before an investigational site can enter a patient into the study, a representative of Institute of Human Virology will visit the investigational study site to:

- Determine the adequacy of the facilities
- Discuss with the investigator(s) and other personnel their responsibilities with regard to protocol adherence, and the responsibilities of the Institute of Human Virology or its representatives. This will be documented in a Clinical Study Agreement between the Institute of Human Virology and the investigator.

During the study, a monitor from the Institute of Human Virology or representative will have regular contacts with the investigational site, for the following:

- Provide information and support to the investigator(s)
- Confirm that facilities remain acceptable
- Confirm that the investigational team is adhering to the protocol, that data are being accurately recorded in the case report forms, and that investigational product accountability checks are being performed
- Perform source data verification. This includes a comparison of the data in the case report forms with the patient's medical records at the hospital or practice, and other records relevant to the study. This will require direct access to all original records for each patient (e.g. clinic charts).
- Record and report any protocol deviations not previously sent to Institute of Human Virology.
- Confirm AEs and SAEs have been properly documented on CRFs and confirm any SAEs have been forwarded to Institute of Human Virology and those SAEs that met criteria for reporting have been forwarded to the IRB.

The monitor will be available between visits if the investigator(s) or other staff needs information or advice.

14.2. Audits and Inspections

Authorized representatives of the Institute of Human Virology, a regulatory authority, an Independent Ethics Committee or an Institutional Review Board may visit the site to perform audits or inspections, including source data verification. The purpose of an Institute of Human Virology audit or inspection is to systematically and independently examine all study-related activities and documents to determine whether these activities were conducted, and data were recorded, analyzed, and accurately reported according to the protocol, Good Clinical Practice guidelines of the International Conference on Harmonization, and any applicable regulatory requirements. The investigator should contact Institute of Human Virology immediately if contacted by a regulatory agency about an inspection.

14.3. Institutional Review Board (IRB)

The Principal Investigator must obtain IRB approval for the investigation. Initial IRB approval, and all materials approved by the IRB for this study including the patient consent form and recruitment materials must be maintained by the Investigator and made available for inspection.

15. Quality Control and Quality Assurance

To ensure compliance with Good Clinical Practices and all applicable regulatory requirements, the Institute of Human Virology may conduct a quality assurance audit. Please see [Section 14.2](#) for more details regarding the audit process.

15.1. Study Monitoring

The study will be monitored by the Sponsor or its representatives in compliance with government regulations and according to good clinical practices and standard operating procedures. Regular telephone contacts and site visits will be made throughout the course of the study. These individuals will have access, both during the trial and after trial completion, to review and audit all records (including original volunteer records, drug accountability and storage, and general study documentation and execution) necessary to ensure integrity of the data, and will periodically review progress of the study with the principal investigator. Every attempt will be made to follow the protocol and to obtain and record all data requested for each volunteer at the specified times. However, ethical reasons may warrant the failure to obtain and record certain data, or to record data at the times specified. If this becomes necessary, the reasons for such must be clearly documented on the case report form.

Monitoring visits will be made on a frequent basis with advanced notification of the study center by the sponsor or its representatives. Study center personnel will be informed of the study documents/records which will be reviewed at each visit. It is expected that monitoring visits will be made approximately every 4 to 12 weeks dependent upon the rapidity of enrollment.

15.2. Laboratory

All safety laboratories will be performed at the University of Maryland Medical Center Clinical laboratories, a CLIA certified laboratory.

All immunology laboratory studies are planned to occur at the IHV Immunology Laboratory, Profectus Biosciences or one or more of the Bill and Melinda Gates Core Laboratories which currently include the Vaccine Research Center, NIH; the Duke Human Vaccine Center, Durham, North Carolina; Harvard's Ragon Institute, Cambridge, MA, or Dartmouth University, Hanover, NH.

15.3. Handling of Biologic Samples

The transmission of retroviruses may occur through contact with contaminated needles and blood or blood products. Consequently universal blood and body fluid precautions should be employed by all personnel involved in drawing of blood and handling of specimens in clinic and laboratory locations. For samples that have to be shipped to other sites, specific regulations regarding intersFLSCe/international shipment apply and these procedures must be adhered to. It is the responsibility of the investigator to ensure that all study specimens are appropriately handled.

1. *Virology Evaluations:* For HIV PCR and other research virology assays, plasma and cells must be collected and processed within 6 hours, and either stored at $< -135\text{ C}^\circ$ for PBMC and $< -70\text{ C}^\circ$ for serum or used by the laboratory investigator in an appropriate time frame.
2. *Immunology Evaluations:* All clinical and research immunological studies must be performed on samples collected and processed within a 6 hour period and stored at $< -135\text{ C}^\circ$ for PBMC and $< -70\text{ C}^\circ$ for serum or provided to the appropriate laboratory

16. Ethics

16.1. Ethics Review

The final study protocol, including the final version of the Informed Consent Form, must be approved or given a favorable opinion in writing by an IRB which is constituted and operates in accordance with Part 56 of Title 21 of the Code of Federal Regulations. The investigator must submit written approval to the Institute of Human Virology before he or she can enroll any patient/subject into the study.

The Principal Investigator is responsible for informing the IRB or IEC of any amendment to the protocol in accordance with local requirements. In addition, the IRB or IEC must approve all advertising used to recruit patients for the study. The protocol must be re-approved by the IRB or IEC upon receipt of amendments and annually, as local regulations require.

The Principal Investigator is also responsible for providing the IRB with reports of any reportable serious adverse drug reactions from any other study conducted with the investigational product. Institute of Human Virology will provide this information to the Principal Investigator.

Progress reports and notifications of serious adverse drug reactions will be provided to the IRB or IEC according to local regulations and guidelines.

17. Ethical Conduct of the Study

The study will be performed in accordance with ethical principles that have their origin in the Declaration of Helsinki and are consistent with ICH/Good Clinical Practice, applicable regulatory requirements and the Institute of Human Virology's policy on Bioethics.

Investigator Responsibilities

The execution responsibility of this protocol rests with the Principal Investigator. The Principal Investigator is responsible for the submission of the AEs, and an assessment of the causal relationship with the treatment. AEs will be recorded using an adverse experience grading system adapted from the ACTG and AVEG tables; all AEs must be recorded in the case report forms with details of the duration and grade of each episode, and the action taken for each event. A serious AE is considered one that results in death, a life threatening adverse drug experience, inpatient hospitalization, a persistent disability/incapacity, or a congenital abnormality/birth defect. All serious adverse experiences, including death, on study or within 30 days of withdrawal, must be recorded on a serious adverse events (SAE) form and sent to the study sponsor.

Protocol Modification

It is essential to the success of the study that the Investigator adhere to both the spirit and the letter of the protocol. Except in the event of a medical emergency or where necessary to protect the safety, rights or welfare of the study volunteer(s), any changes to the protocol will require the prior written approval of the sponsor, the IHV. In the case of a minor deviation from protocol, a letter from the Sponsor will suffice. Changes to the protocol affecting study objectives, study design, volunteer population, study procedures or significant administrative aspects will require that the protocol be formally amended. Protocol amendments will be made only after having been agreed to by the investigators and IHV. All formal amendments must be approved by the Institutional Review Board (IRB) prior to implementation.

17.1. Written Informed Consent

Volunteer

The volunteer will be informed of the nature of the study agent and its intended purpose; study procedures and associated risks will be explained as well as possible adverse experiences. Written informed consent shall then be obtained from each volunteer, in accordance with FDA regulations set forth in Part 50 of Title 21 of the Code of Federal Regulations, prior to entering the volunteer into the trial or prior to performing any unusual or non routine procedure that involves risk to the volunteer. The investigator shall provide a copy of the current IRB-approved informed consent to the volunteer and a signed copy shall be maintained in the volunteer's record file. The informed consent will be written in accordance with US Federal Regulations for Protection of Human Subjects (21 CFR 50.25[a] and 21 CFR 50.25[b]).

Investigator

The Principal Investigator(s) at each center will ensure that the patient is given full and adequate oral and written information about the nature, purpose, possible risk and benefit of the study. Patients must also be notified that they are free to discontinue from the study at any time. The patient should be given the opportunity to ask questions and allowed time to consider the information provided.

The patient's signed and dated informed consent must be obtained before conducting any study procedures.

The Principal Investigator(s) must maintain the original, signed Informed Consent Form. A copy of the signed Informed Consent Form must be given to the patient.

18. DATA HANDLING AND RECORDKEEPING

18.1. Inspection of Records

Institute of Human Virology will be allowed to conduct site visits to the investigation facilities for the purpose of monitoring any aspect of the study. The Investigator agrees to allow the monitor to inspect the drug storage area, study drug stocks, drug accountability records, volunteer charts and study source documents, and other records relative to study conduct. In addition, representatives of the Food and Drug Administration (FDA) and the Institutional Review Board (IRB) shall have access to the source data and documents when requested. During any document reviews, volunteer anonymity will be maintained with strict adherence to professional standards of confidentiality.

18.2. Retention of Records

The Principal Investigator must maintain all documentation relating to the study for a period of 2 years after the last marketing application approval, or if not approved 2 years following the discontinuance of the test article for investigation. If it becomes necessary for Institute of Human Virology or the Regulatory Authority to review any documentation relating to the study, the Investigator must permit access to such records.

18.3. Data Recording

Source documents of all data will be maintained in the volunteer's research clinical record. In addition Case Reports Forms (CRF) will be created and maintained for each volunteer utilizing REDCap(Research Electronic Data Capture) software. All study data will be recorded on the Case Report Forms (CRFs). REDCap tracks all data corrections made by authorized users, providing audit trails for monitoring or query.

Any information that is not obtained as specified in the protocol should be indicated by the designation ND for not done or NA for not applicable. An explanation should be noted on the case report form as to why the required information was not obtained.

18.4. Data Control Methods

In order to assure adequate control and provide study data which are consistent and of the highest quality, the following measures will be employed:

- Each clinical procedure (*e.g.* physical examination) for a particular volunteer will be conducted by the same person, if possible, throughout the volunteer's study participation;
- Data automatically generated will be acceptable only after review by the appropriate specialist; for example, computer-generated EKG interpretation must be signed off by a cardiologist.
- Adverse Events will be both volunteered by the volunteer and specially elicited by questioning. Careful unbiased monitoring of volunteers for development of adverse experiences will be essential throughout the study. Volunteers will be questioned at every clinical visit in order to detect toxicity, however mild. Volunteer interviews must be conducted in a non-leading way (*e.g.* "How have you been feeling since your last clinic visit; have you noticed anything out of the ordinary?"). Questions may be specific to symptoms previously reported in order to follow ongoing complaints.

19. PUBLICATION POLICY

All personnel involved in the study shall not disclose or use for any purpose any data, records, and other information related to the study until approved by Principal Investigator. The data shall be confidential until publication. Any publication or presentation related to the trial must be approved by the Institute of Human Virology before submission of the manuscript.

21. APPENDICES

APPENDIX 1. DETAILED REACTOGENICITY FORM

(Note these are the items which will be on the diary card given to each volunteer after each immunization to record any events occurring in the first 7 days following each immunization.)

PATIENT NAME: _____ DATE: _____
STUDY NUMBER: _____ STUDY DAY: _____ NURSE: _____

PLEASE ENTER ANY SYMPTOMS YOU MAY HAVE WITHIN 48 HOURS AFTER YOUR VACCINE INJECTION IN THE COLUMN BESIDE IT. MAIL IT IN THE ENVELOPE PROVIDED (CIRCLE Y OR N)

SYMPTOM	YES/NO	ONSET (m/d/y)	DURATION (hours)
FEVER	Y	N	
CHILLS	Y	N	
NAUSEA	Y	N	
VOMITING	Y	N	
JOINT PAINS (arthralgia)	Y	N	
MUSCLE ACHES (myalgia)	Y	N	
FATIGUE (malaise)	Y	N	
HIVES OR RASH (urticaria)	Y	N	
WHEEZING	Y	N	
HEADACHES	Y	N	
ITCHING	Y	N	
PAIN	Y	N	
DIARRHEA	Y	N	
OTHER	Y	N	

*PLEASE CALL YOUR PROTOCOL NURSE/PHYSICIAN IF YOU SHOULD HAVE ANY OF THE SIGNS AT THE INJECTION SITE ON THIS LIST (CIRCLE Y OR N).

SYMPTOM	YES/NO	ONSET (m/d/y)	DURATION (hours)
REDNESS (erythema)	Y N		
ROUGHNESS (induration)	Y N		
SWELLING	Y N		
NODULE (subcutaneous)	Y N		
TENDERNESS	Y N		
SKIN BREAKDOWN	Y N		
SWOLLEN OR TENDER LYMPH NODES UNDER YOUR ARM	Y N		
INABILITY TO MOVE OR USE ARM	Y N		
OTHER	Y N		

Reviewed by _____ (Protocol Nurse)

Reviewed by _____ (Study MD)

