6.1.1.3. Study Evaluations

See also the Schedule of Assessments in [Table 4](#).

1. Study Visit 0, Day –30 to Day –3 (Week –4 to 0): Screening Visit

A screening evaluation will be performed within 3-30 days of the first immunization to determine eligibility for the study and to collect blood for baseline safety evaluation and immunological exams.

- a. Obtain informed consent for study prior to screening
- b. Obtain and record medical history including allergies, medications, and concomitant illnesses, and review of systems
- c. Counsel volunteer regarding avoiding HIV risk behaviors
- d. Perform complete physical examination, including vital signs, temperature, weight and height.
- e. Collect blood for CBC with differential, serum chemistries, liver function tests (including AST, ALT, alkaline phosphatase, total bilirubin), PT/PTT, CD4 cell count, Hepatitis B surface antigen, Hepatitis C antibody, HIV-1 ELISA/Western Blot, HIV-1 quantitative RNA PCR, and, in women, serum human chorionic gonadotropin (HCG) assay (See [Table 4](#) and [Section 11](#)).
- f. Collect urine for urinalysis
- g. Collect blood for baseline immunologic exams (See [Table 5](#) and [Section 12](#))

2. Study Visit 1, Day 0 (Week 0): First Immunization

- a. Obtain interim medical history since screening visit
- b. Perform physical examination, including vital signs, temperature, weight and height.
- c. Conduct urine pregnancy test (female volunteers).

If volunteer continues to meet inclusion/exclusion criteria he/she will be given a volunteer number, randomized, and the following will be done:

- d. Collect blood for safety labs (CBC with differential, serum chemistries, LFT's, CD4 cell count, and Quantitative HIV-1 RNA PCR) ([Table 4](#), [Table 5](#) and [Section 11](#)).
- e. Collect blood for immunologic studies ([Table 4](#) and [Table 5](#) and [Section 12](#)).
- f. Administer first injection of the study vaccine as an intramuscular injection in the deltoid muscle as per [Section 9.5](#).
- g. Record vital signs and examine injection site for local reactions at 15 and 30 minutes post-injection.
- h. Observe and instruct while volunteer takes own temperature and assesses local reactions (as a guide for subsequent evaluations at home).
- i. Counsel volunteer regarding avoiding HIV risk behaviors
- j. Dispense diary for immunization reactions ([Appendix 1](#)) and digital thermometer. Give instructions for diary completion and thermometer use.

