11.1.5.6. Assessment of Vaccine Reactogenicity

The safety evaluation will include an evaluation of both local and systemic reactions to the candidate immunotherapeutic vaccines. Assessment of local reactogenicity will include erythema, induration, swelling, itching, pain and tenderness, skin discoloration, skin breakdown, and presence of subcutaneous nodules at the site of injection. Assessment of systemic reactions will include assessment of fever, chills, nausea, vomiting, arthralgia, myalgia, malaise, urticaria, wheezing, dizziness, headache. Each volunteer will complete a self-administered questionnaire/diary daily for 7 days after each immunization to assess reactogenicity. In addition, follow up telephone contact or clinic visit will be conducted by research nurse 24 to 48 hours following each immunization to record reactogenicity/adverse events. The study personnel will also conduct a careful assessment of possible adverse experiences at each clinic visit (See [Table 4](#)). Both the volunteer diary and the elicited adverse experiences will be used to determine the occurrence of adverse events. Any discrepancies between these sources will be resolved by careful review of the data with the volunteer. All adverse events will be recorded in the CRFs as noted in [Section 11.4](#).

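### The diary card asks volunteers for symptoms within 48 hours, where Section 11.1.5.6 requires a daily 7-day diary, and it has no field for the temperature reading that fever grading needs

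*Combined protocol and SAP*

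**What the plan says.** Section 11.1.5.6 sets the diary requirement: "Each volunteer will complete a self-administered questionnaire/diary daily for 7 days after each immunization to assess reactogenicity". It also gives the diary a role in ascertainment: "Both the volunteer diary and the elicited adverse experiences will be used to determine the occurrence of adverse events". The note at the head of Appendix 1 agrees on the period, saying that the card is there "to record any events occurring in the first 7 days following each immunization".

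The line on the card that addresses the volunteer says something else: "PLEASE ENTER ANY SYMPTOMS YOU MAY HAVE WITHIN 48 HOURS AFTER YOUR VACCINE INJECTION IN THE COLUMN BESIDE IT". Below it is a list of 14 mainly systemic items. A second list of 9 injection-site items follows, with no time window and its own instruction: "PLEASE CALL YOUR PROTOCOL NURSE/PHYSICIAN IF YOU SHOULD HAVE ANY OF THE SIGNS AT THE INJECTION SITE ON THIS LIST". Both lists have the same columns: symptom, yes/no, onset date and duration in hours.

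Three other parts of the plan bear on this:

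- **Staff contact (11.1.5.6 and 6.1.1.3).** A "follow up telephone contact or clinic visit will be conducted by research nurse 24 to 48 hours following each immunization", and that call asks for the oral temperature. The diary is reviewed at Visits 2, 4, 6 and 10.
- **Thermometer (6.1.1.3, Visit 1).** Staff hand out a digital thermometer with the diary and are told: "Give instructions for diary completion and thermometer use".
- **Endpoint and grading (13.4, Appendix 2).** The primary reactogenicity endpoints are severe systemic and severe local reactions. The fever row of Appendix 2 applies to oral temperature over more than 12 hours. Grade 2 is 38.6 to 39.5C and Grade 3 is 39.6 to 40.5C.

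**The concern.** A volunteer who follows the card as printed has no reason to write down a systemic reaction that begins on the third day or later. Such a reaction is then absent from one of the two sources that 11.1.5.6 uses to decide whether an adverse event occurred. If the reaction is a fever, the card has nowhere to put the number that determines its grade, even though the volunteer has been given a thermometer.

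The grades matter beyond the comparison in 13.4. A stopping criterion in 6.4.1 counts vaccine-related Grade 3 or 4 events, and dose escalation under 6.4 depends on DSMB review of safety data through Visit 4. This is a remark about what depends on the data, not about those rules. The same card goes to vaccine and placebo recipients, so any loss affects both.

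**Working it through.** The plan gives no figure for diary capture, so there is none to reproduce. The detectable rates in 13.1 concern SAE rates and do not depend on the card. The check is a comparison of texts, a count of items and simple date arithmetic.

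**1. Window.**

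| Place | Addressed to | Period |
|---|---|---|
| 11.1.5.6 | protocol reader | daily, 7 days |
| Appendix 1, heading note | protocol reader | first 7 days |
| Appendix 1, first list | volunteer | 48 hours |
| Appendix 1, injection-site list | volunteer | none stated; call the nurse or physician |

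The required period is 7 × 24 = 168 hours. The part outside the card's instruction is 168 − 48 = 120 hours, and this applies after each of the four doses.

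**2. Which signs are affected.** Section 11.1.5.6 names 9 local signs (erythema, induration, swelling, itching, pain, tenderness, skin discoloration, skin breakdown, nodules) and 11 systemic signs, 20 in all.

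- The first card list holds 10 of the 11 systemic signs. It also has itching and pain, not labelled as injection-site. Under the 48-hour line: 10, or 10 + 2 = 12 if those two rows are read as local signs.
- The injection-site list holds 6 of the local signs, with no window.
- Dizziness and skin discoloration have no row and can go only under OTHER.
- Check: 12 + 6 + 2 = 20.

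**3. Layout and fields.** Each symptom has one row, so the card is not laid out for daily entries. The duration column can show whether a fever lasted more than 12 hours. Nothing on the card can show whether it was 39.5C or 39.6C, the boundary between Grade 2 and Grade 3.

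**4. What else is scheduled.** The only scheduled request for a home temperature reading is the call at 24 to 48 hours. The next contact is the diary-review visit: 14 − 0 = 42 − 28 = 70 − 56 = 182 − 168 = 14 days after each dose, or hour 14 × 24 = 336. For a reaction outside the card's window:

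- onset at hour 48: 336 − 48 = 288 hours = 12 days before the visit;
- onset at hour 168: 336 − 168 = 168 hours = 7 days before the visit.

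The interval is therefore 7 to 12 days when the dose and the visit are on schedule.

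**The case against.** The best defence is that the card is not the only safeguard. Staff explain the diary at every dose and may give the 7-day period orally. Section 9.5 tells volunteers to call at once about any adverse event after leaving the clinic, and the card repeats this for injection-site signs. Section 18.4 requires questioning about toxicity at every clinical visit, and 11.1.5.6 has discrepancies resolved with the volunteer. A reaction that starts early and persists is caught by the duration column. The endpoint is *severe* reactions, which people are least likely to forget or leave unreported.

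All of this stands, and it limits the consequence. It does not remove the conflict. Oral instructions would have to contradict the printed line, and neither a call nor a later interview supplies a written temperature series.

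A second defence is that the investigator grades severity under 11.4, 11.5.1 and Appendix 2, so the card need not ask volunteers to rate it. That is right. A self-rated severity column is a preference, and its absence is not an error. The temperature field is different, because it holds a measurement that the grading table requires.

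The appendix might also be only a sketch of the final card. But its heading note says that these are the items the card will carry, and both tables show the same complete set of columns.

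**Conclusion.** The point holds as an internal contradiction with a gap in one form, and it should be fixed. Appendix 1 and 11.1.5.6 disagree on the recording period (48 against 168 hours) for 10 to 12 of the 20 named signs, and the card cannot hold the reading that grades a fever. The likely effect is some under-capture or under-grading of late-onset reactions. The documents give no onset distribution, so its size cannot be computed. The conclusion assumes that the printed card follows Appendix 1 and that volunteers follow the card. The 7 to 12 days assume on-time doses and visits.

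A reader might infer more than the documents support:

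- **That 120 of 168 hours means most reactions are lost.** The ratio counts hours, not reactions, and early-onset reactions that persist are still recorded.
- **That severity goes uncollected, or the 13.4 endpoint cannot be assessed.** The investigator grades every adverse event, and the call and the visits supply history.
- **That severe local reactions have no scale.** The Local Reaction row of Appendix 2 excludes vaccination. But 11.4 sends all adverse events to Appendix 2, whose generic scale covers anything not listed and defines severe.
- **That "MAIL IT IN THE ENVELOPE PROVIDED" conflicts with diary review at the visit.** A mailed card can be reviewed there.
- **That recall of three weeks or more is typical.** The windows in 6.1.1.4 allow late visits, but that figure also needs the volunteer not to have called. It is a stacked worst case and no measure of the problem.

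**What to change.** Revise Appendix 1 in three ways:

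1. Replace the 48-hour line with an instruction that matches 11.1.5.6, asking for daily entries for 7 days on both lists, and lay the card out by day.
2. Add a field for the measured oral temperature.
3. Add rows for dizziness and skin discoloration, which 11.1.5.6 names.

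A field for limitation of activity or severity, to support the investigator's grading, is optional.

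The cost is one form revision with IRB approval and a few more minutes of diary time for the volunteer. No visits or staff are added, and no sample size or analysis changes. As a clerical correction at the same time, 13.2 cites Appendices 1 and 3 for adverse reactions, but Appendix 3 is the drug accountability policy.
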